**Study start: July 17, 2020**

**Primary completion: October 1, 2021**

**Study completion: October 2, 2021**

#### **Brief summary**

A retrospective consecutive population of patients treated with conical tapered stems in cementless total hip arthroplasty for osteoarthritis due to congenital hip pathologies will be selected. The aim of this retrospective study is to evaluate the long-term clinical and radiographic results of this implant and the survival rates in such a specific cohort.

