#### **Study description**

Congenital hip pathologies may severely alter the local anatomy of the hip, making total hip arthroplasty (THA) due to osteoarthritis after congenital hip pathologies challenging. While it seems that congenital hip pathologies did not significantly influence the outcomes when compared to THA after osteoarthritis, the choice of implant was demonstrated to impact the survival rates of the THA after congenital hip pathologies.

To date, no guidelines exist about the correct choice of hip implant in congenital hip pathologies: only mid-term case series are available. Conical tapered stems have been frequently suggested for the most difficult cases.

The aim of this study is to describe the survival rates and the long-term clinical and radiological outcome of conical tapered stems in THAs after congenital hip pathologies.

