#### **Population**

retrospective, consecutive adult population treated with conical tapered stems in cementless total hip arthroplasty for osteoarthritis due to congenital hip pathologies.

Inclusion Criteria:

Symptomatic hip osteoarthritis due to congenital hip pathologies

Consecutive population with a minimum follow-up of 2 years

Cementless total hip arthroplasty with conical tapered stem

Pre-operative planning using CT

Complete clinical and radiographic assessment

Exclusion Criteria:

Other type of hip osteoarthritis

Other type of implants

Inadequate pre-operative planning (eg: no CT)

Incomplete clinical and radiographic assessment

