#### **Methods**

Demographics of the patients involved were collected using medical records.

The patients were clinically and radiographically evaluated in the post-operative setting at 1, 6, 12, 24 months and then biennial. Harris Hip score (HHS) was adopted to clinically assess the patients at the final follow-up []. Plain antero-posterior pelvis radiographs were taken at every follow-up: the last X-ray was evaluated for the positional parameters specified in the table []. Osseointegration was evaluated using the criteria of Moore et al. (cup) and Engh et al. (stem) [].

Failures were collected and the survival rates were specified, using a 95% confidence interval.

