#### **Statistical analysis plan**

Statistical analysis has been done by using Windows SPSS 14.0, 14.0.1 version (SPSS Inc, Chicago, IL) and JMP, 12.0.1 version (SAS Institute Inc, Cary, NC, 1989-2007).

The quantitative data were expressed as average values, standard deviations and ranges of minimum and maximum. The qualitative data were expressed as frequencies and percentages. The survivorship of the primary THA implants were calculated and plotted according to Kaplan-Meier method (95% confidence interval). The endpoint was removal or change of any component. The implants were followed until the last date of observation (date of death or 31 December 2019). A p-value less than 0.05 was considered statistically significant.

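### The aim names survival of the conical tapered stem, but the only planned survival analysis counts revision of any hip component, so stem survival is never estimated

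*Combined protocol and SAP*

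**What the plan says.** The Study description gives the aim as to "describe the survival rates and the long-term clinical and radiological outcome of conical tapered stems in THAs after congenital hip pathologies". The Brief summary is looser: it wants to "evaluate the long-term clinical and radiographic results of this implant and the survival rates in such a specific cohort". The Study description also offers a rationale at the level of the whole hip replacement, namely that "the choice of implant was demonstrated to impact the survival rates of the THA after congenital hip pathologies".

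The Population section defines the implant by "Cementless total hip arthroplasty with conical tapered stem" and names no cup, liner, head or bearing.

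On survival, the Methods section says only that "Failures were collected and the survival rates were specified, using a 95% confidence interval". The detail is in the Statistical analysis plan: "The survivorship of the primary THA implants were calculated and plotted according to Kaplan-Meier method", with a 95% confidence interval. The event is given in one sentence: "The endpoint was removal or change of any component". Follow-up runs to death or 31 December 2019.

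The components are separated in one place, the radiographic assessment in the Methods section. There, "Osseointegration was evaluated using the criteria of" two published systems, one for the cup and one for the stem.

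**The concern.** The survival analysis measures a broader object than the one the aim names. A worn liner exchanged around a well-fixed stem, or a loose cup revised with the stem left in place, is a full failure in the only survival curve of a study about a stem.

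The consequence depends on the result. If construct survival is high, a favourable statement about the stem is safe, because stem survival can only be higher. If it is poor, the curve cannot show whether the stem or another component was responsible. In either case a surgeon choosing a stem, the reader suggested by the document's remarks on the lack of guidance on implant choice, receives no stem survival figure and no measure of its uncertainty.

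**Working it through.** The documents state no sample size, event count or survival rate, so there is no figure of the plan's own to reproduce. The check compares the sections and then illustrates the possible gap on assumed inputs.

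**1. Aim against analysis**

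| Element | Section | Level |
|---|---|---|
| Aim | Study description | Stem |
| Aim, shorter form | Brief summary | This implant; survival in the cohort |
| Selection by implant | Population | Stem and cementless fixation |
| Osseointegration | Methods | Cup and stem separately; not time-to-event |
| Failures and survival | Methods | No component named |
| Kaplan-Meier event | Statistical analysis plan | Any component |

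No row provides a time-to-event analysis of the stem.

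**2. Direction of the difference**

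Every stem revision is also an any-component revision, so a hip's time to any-component revision is never later than its time to stem revision. With the same censoring, S_any(t) ≤ S_stem(t) at every time t. The planned curve is a lower bound.

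**3. Size, on assumed inputs**

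Let p be the stem's share of the revision hazard, assumed constant over time, and assume that the stem hazard is unchanged after a non-stem revision. The cumulative hazard is H_any = −ln(S_any). Then H_stem = p × H_any, and S_stem = exp(−p × H_any) = S_any^p.

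For example, with S_any = 0.90 and p = 0.50: 0.90^0.50 = 0.949, a gap of 94.9 − 90.0 = 4.9 points.

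| Assumed S_any | p = 0 | p = 0.25 | p = 0.50 | p = 0.75 | p = 1 |
|---|---|---|---|---|---|
| 95% | 100% (gap 5.0) | 98.7% (3.7) | 97.5% (2.5) | 96.2% (1.2) | 95% (0) |
| 90% | 100% (gap 10.0) | 97.4% (7.4) | 94.9% (4.9) | 92.4% (2.4) | 90% (0) |
| 80% | 100% (gap 20.0) | 94.6% (14.6) | 89.4% (9.4) | 84.6% (4.6) | 80% (0) |

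Cells show stem survival, with the gap in percentage points. The gap is zero only if every revision involves the stem. It equals the whole any-component failure rate if none does.

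**4. Precision a stem analysis might have**

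The number of hips and events is again assumed, with no censoring before the time point. The Greenwood variance of ln S is then (1 − S)/(nS). The log-log 95% interval is S^exp(±1.96 × se), with se = √[(1 − S)/(nS)] / |ln S|.

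For 100 hips and 5 stem revisions, se = √(0.05/95)/0.0513 = 0.447, and exp(1.96 × 0.447) = 2.40. The limits are 0.95^2.40 = 88.4% and 0.95^(1/2.40) = 97.9%.

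| Hips | Events | Estimate | 95% CI |
|---|---|---|---|
| 50 | 2 stem | 96.0% | 84.9% to 99.0% |
| 100 | 5 stem | 95.0% | 88.4% to 97.9% |
| 200 | 10 stem | 95.0% | 90.9% to 97.3% |
| 100 | 10 any-component | 90.0% | 82.2% to 94.5% |

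**The case against.** The best defence is that the mismatch rests on one sentence. The Brief summary speaks of survival in the cohort, the rationale speaks of survival of the hip replacement, and the analysis plan fits both. On that reading the aim is loosely worded and no analysis is missing. This has some force, and it is why the construct endpoint should stay. It does not dispose of the point: the Study description contains the one explicit statement of the aim, its survival rates belong to the stem, and the stem is the only component that defines the cohort. Even if construct survival was all that was meant, the two sections would need to be aligned.

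A second defence is that the planned estimate cannot flatter the stem, and that no comparison or survival threshold depends on it. That is correct and limits the harm. A lower bound still does not estimate the quantity named.

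Third, a listing of failures by component would fit the descriptive plan and would help to attribute a poor result. It would, but no section specifies one, and it would not supply a survival estimate that allows for unequal follow-up.

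Fourth, the size of the gap is hypothetical and its range includes zero, and the added curve may rest on very few events. Both are true. The case for the change therefore rests on the unanswered aim and the low cost of answering it, and not on any claimed size of bias.

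**Conclusion.** The concern holds. Followed as written, the plan yields a valid estimate of construct survival and none of stem survival, which the Study description names as the aim. The existing analysis is not wrong; it is incomplete for the question asked. This should be corrected, but it does not invalidate the study.

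The direction is certain: construct survival cannot exceed stem survival. The size is not known from the documents. Across assumed construct survival of 80% to 95%, the gap runs from 0 to 20 points, depending on how many revisions involve the stem. These figures assume a constant stem share of the hazard and a stem hazard unaffected by earlier non-stem revisions.

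**What to change.** In the Statistical analysis plan:

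- Keep any-component revision and label it as survival of the construct.
- Add one Kaplan-Meier analysis, with a 95% confidence interval, for removal or change of the femoral stem for any reason. A hip with only a cup, liner or head change stays at risk. Follow-up is censored at death or 31 December 2019, as now.
- Tabulate all failures by component revised and by cause.
- Base statements about the stem on the stem endpoint. A further curve for stem revision for aseptic loosening is optional.

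Rewording the aim to survival of the whole hip replacement would remove the inconsistency on paper, but it would give up the stem question.

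The cost is one further Kaplan-Meier run and one table, with no new patient contact. Two checks come first, because the Methods section says only that failures were collected: that the records identify the component revised, and that stem status is known after a first non-stem revision. The main drawback is that there may be few stem events and a wide interval, which should be reported as such.
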